### **12.3. Discontinuation of Study Drug**

Study drug will be discontinued if any of the following events occur during the study:

- A patient suffers an AE that, in the judgment of the investigator, sponsor, or medical monitor, presents an unacceptable risk to the patient
- General or specific changes in the patient's condition (eg, a significant intercurrent illness or complication) that, in the judgment of the investigator, are unacceptable for further administration of study drug
- Occurrence of pregnancy
- Significant noncompliance with protocol requirements
- The sponsor or legal representative of the sponsor requests the patient to withdraw
- Patient has radiologically documented disease progression

In the event of study drug discontinuation, patients should be strongly encouraged to complete all scheduled assessments through the end of their current 21-day treatment cycle, including the PRO scales; CBC assessment on Day 22; the Post-Treatment Visit; and the Survival Follow-up Phase of the study. A patient who discontinues study treatment for reasons other than PD will have a CT or MRI scan at the Post-Treatment Visit, if they have not had a scan within the prior 4 weeks.

The investigator will document the reason for study drug discontinuation on the applicable eCRF page.

When discontinuation is due to a SAE or a Grade 3 or 4 toxicity considered to be related to study medication, the investigator should follow the event until resolution, return to baseline,

or it is deemed that further recovery is unlikely. Data on these events should be collected on the AE CRF.

In the event a patient discontinues due to an AE or pregnancy, the investigator should notify the medical monitor by telephone within 48 hours of study drug discontinuation.

#### **12.4. Withdrawal of Patients from the Study**

Patients may withdraw from the study at their own discretion (or at the discretion of the investigator) for any reason at any time. The following list of reasons for withdrawing patients from the study may include but are not limited to:

- Withdrawal of informed consent
- Lost to follow-up (must have at least 2 documented attempts to contact the patient; 1 attempt must be written to the patient and sent via certified letter)
- If central pathology review does not confirm SCLC diagnosis, the patient may be withdrawn from the study after consultation between the principal investigator, medical monitor, and sponsor

All data collected prior to the date of withdrawal of consent will remain in the clinical database.

## **13. STATISTICS**

Full details on the statistical analyses to be performed will be provided in a separate statistical analysis plan (SAP).

### **13.1. Sample Size and Power**

The sample size for this study is determined by clinical rather than statistical considerations. Up to 40 patients (open-label, dose-finding cohort[s] and an open-label, expansion cohort) will be enrolled in Part 1 of the study and 70 patients will be enrolled in Part 2 of the study (randomized). With 35 patients, the precision for point estimates in each arm is as follows: the 95% confidence interval (CI) width for binary endpoints based on Wilson score intervals are at most the observed proportion  $\pm 0.157$ . The 95% CI width for continuous endpoints using the t-distribution are the observed mean  $\pm 0.344$ \*standard deviation of the endpoint.

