### 13.2.3. General Considerations for Data Analysis

All statistical analyses will be performed using SAS® version 9 or higher.

Data will be summarized separately by study part (Part 1 and Part 2). Data from Part 1 will be summarized descriptively by dose level if applicable and overall. Data from Part 2 will be summarized descriptively by treatment group and overall. Treatment differences between treatment groups for Part 2 will be calculated as G1T28 + E/P therapy minus placebo + E/P therapy. Select safety summaries will include combined data from both Part 1 and Part 2 of the study. The descriptive summary for the categorical variables will include counts and percentages. The descriptive summary for the continuous variables will include means, medians, standard deviations, and minimum and maximum values. The descriptive summaries of time to event data will include median, twenty-fifth and seventy-fifth percentiles and standard error. All data will be listed for all patients. Unless specified otherwise, safety summaries will include all collected data, and summaries of efficacy will include data collected through the Treatment Phase.

This study is descriptive in nature, and no formal hypothesis testing will be performed across treatment groups. All CIs will be 95%, unless stated otherwise.

The effects of covariates and withdrawal from study treatment due to reasons other than death, disease progression, and toxicity will be assessed to determine the impact on the general applicability of results from this study. Further details of the analysis, including the handling of missing data, impact of variable chemotherapy dose exposure including dose reductions, transformations and other data handling procedures will be provided in a separate SAP. Exploratory analyses of the data will be conducted as deemed appropriate.

Summaries that are based on within-cycle, including changes, events, or findings, will require a clear definition of “end of cycle” that accounts for variable durations in the cycle due to within-cycle dosing delays, delays in subsequent cycle initiation, and incomplete cycles. This will be discussed in the SAP for each applicable endpoint.

Protocol violations will be fully defined and documented before unblinding.

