2.3. Number of Patients

Overall, up to 110 patients will be enrolled in the study. The sample size for this study is determined by clinical rather than statistical considerations.

In Part 1, approximately 40 patients will be enrolled, assuming up to 3 cohorts. Cohorts will consist of 6 patients each in the Phase 1b dose-finding portion of Part 1 and up to 18 patients in the Phase 2a expansion portion of Part 1 at the selected dose to be used in Part 2. Additional patients may be enrolled in the Phase 1b dose-finding portion of Part 1 if more than 1 cohort is enrolled. In Part 2, 70 patients will be randomly assigned (1:1 ratio) to 1 of 2 groups: G1T28 administered IV with E/P therapy (Group 1) or placebo administered IV with E/P therapy (Group 2). With 35 patients, the precision for point estimates in each arm is as follows: the 95% confidence interval (CI) width for binary endpoints based on Wilson score intervals are at most the observed proportion ± 0.157 . The 95% CI width for continuous endpoints using the t-distribution are the observed mean ± 0.344 *standard deviation of the endpoint.

The study will be conducted at up to 80 centers in North America and Europe.

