The number and percentage of patients in each category of TPR according to the investigator tumor assessment (CR, PR, SD, PD, or NE) will be presented. Also, the number and percentage of patients in each category of derived BOR (Confirmed CR, Confirmed PR, SD, PD, or NE), ORR, ORR_{UNCONFIRMED} and CBR according to the investigator tumor assessment (Confirmed CR, Confirmed PR, SD, PD, or NE) will be summarized. Detailed information of deriving tumor relevant responses is provided in [Section 5.2.6](#).

Similar analyses will be repeated based on the derived responses according to the RECIST 1.1, and based on the data from BICR. A cross tabulation of BICR BOR versus the derived BOR will be presented, by treatment group.

Estimates of response rate, along with its associated exact 95% two-sided CIs using Clopper-Pearson method will be computed for ORR and CBR within each treatment group.

DOR (investigator, derived, and BICR) will be summarized using the Kaplan-Meier method, displayed graphically when appropriate, and summarized with median, 25% and 75% percentiles, and their 95% CIs.

The binary endpoint (Yes, No) of ORR for the two treatments (trilaciclib and placebo) in Part 2 will be analyzed to compare trilaciclib and placebo using stratum-adjusted method to account for the ECOG status (0-1 vs 2) as the stratification factor. The adjusted proportion difference (trilaciclib vs placebo) and its 80% CIs will be calculated using CMH weight outlined in [Kim et al. 2013](#). The two-sided p-value will be calculated using stratified exact CMH method.

The analyses are based on the response evaluable population and FAS population. The supportive data listings will also be provided.

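### The per-arm precision of ± 0.157 for binary endpoints is a Wilson half-width, not a bound around the observed proportion, and is slightly too favourable for the Clopper-Pearson intervals the SAP names

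*Protocol*

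**What the plan says.** Protocol 13.1 opens its sample-size section with "The sample size for this study is determined by clinical rather than statistical considerations". It then describes what the randomised part will yield: "With 35 patients, the precision for point estimates in each arm is as follows", namely that "the 95% confidence interval (CI) width for binary endpoints based on Wilson score intervals are at most the observed proportion" ± 0.157, followed by a bound for continuous endpoints. The binary bound is repeated in SAP 2.3: "width for binary endpoints based on Wilson score intervals are at most the observed proportion ± 0.157". The per-arm number follows from SAP 2.3, where "70 patients will be randomly assigned (1:1 ratio) to 1 of 2 groups".

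No SAP analysis section names a Wilson interval. For per-arm binary results, SAP 6.2.8.7 (Analyses of Objective Response) gives response-rate estimates "along with its associated exact 95% two-sided CIs using Clopper-Pearson method will be computed for ORR and CBR" in each treatment group. The eight prospectively defined binary endpoints in SAP 6.2.7.1 get an 80% interval for an ECOG-adjusted difference between arms. So does the ORR comparison in SAP 6.2.8.7. No per-arm interval is specified for those eight endpoints.

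**The concern.** A Wilson interval is not centred on the observed proportion. A bound written as the observed proportion plus or minus a constant therefore needs the largest distance from that proportion to either limit, which exceeds the largest half-width. The sentence gives the half-width and also calls it a width.

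The sentence also describes a different interval from the one the SAP plans for ORR and CBR. Clopper-Pearson intervals are wider than Wilson intervals at this sample size for every count in the middle of the range.

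At stake is the accuracy of the only figure in either document that tells a reader how precisely a proportion will be estimated with 35 patients. No decision rule or analysis depends on it.

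**Working it through.** **Inputs.** n = 35 per arm (Protocol 13.1; 70 patients at 1:1 in SAP 2.3). Two-sided 95% level, so z = 1.960, z² = 3.8415 and z²/n = 0.10976.

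**1. Reproduce the plan's figures.** The Wilson half-width is

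h = z·√(p(1−p)/n + z²/(4n²)) / (1 + z²/n).

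At p = 0.5: √(0.25/35 + 3.8415/4900) = √(0.007143 + 0.000784) = 0.08903. Then 1.960 × 0.08903 / 1.10976 = 0.1572, so 0.157 reproduces as the maximum half-width. The companion figure for means also reproduces: t(0.975, 34)/√35 = 0.3435, or 0.344.

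**2. Where the Wilson interval is centred.** The centre is (p + z²/2n)/(1 + z²/n). Its shift from the observed proportion is (0.5 − p) × 0.10976/1.10976 = (0.5 − p) × 0.0989. The farther limit is therefore h + 0.0989 × |0.5 − p| from the observed proportion.

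At 12/35 = 0.3429: h = 0.1501 and the shift is 0.1571 × 0.0989 = 0.0155, so the upper limit is 0.1501 + 0.0155 = 0.1656 away.

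**3. All 36 possible counts.** Both intervals were enumerated for x = 0 to 35. Selected rows follow; counts of 18 and above mirror these.

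| x/35 | Wilson 95% | Farther limit | Clopper-Pearson 95% | Half-width | Farther limit |
|---|---|---|---|---|---|
| 6 (0.171) | 0.0810 to 0.3268 | 0.1554 | 0.0656 to 0.3365 | 0.1354 | 0.1651 |
| 7 (0.200) | 0.1004 to 0.3589 | 0.1589 | 0.0844 to 0.3694 | 0.1425 | 0.1694 |
| 12 (0.343) | 0.2083 to 0.5085 | 0.1656 | 0.1913 to 0.5221 | 0.1654 | 0.1793 |
| 17 (0.486) | 0.3299 to 0.6443 | 0.1586 | 0.3138 to 0.6601 | 0.1731 | 0.1744 |

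- Wilson: the farther limit is more than 0.157 away for x = 7 to 28, which is 22 of 36 counts. The maximum is 0.166, at 12/35 and 23/35.
- Clopper-Pearson half-width: above 0.157 for x = 10 to 25 (16 counts), maximum 0.173 at 17/35 and 18/35.
- Clopper-Pearson farther limit: more than 0.157 away for x = 5 to 30 (26 counts), maximum 0.179.

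**4. Size of the discrepancy.** Wilson: 0.166 − 0.157 = 0.009. Clopper-Pearson: 0.173 − 0.157 = 0.016 on half-width and 0.179 − 0.157 = 0.022 on distance.

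**5. Between-arm difference, for reference.** With both rates assumed to be 0.5 and a simple unstratified Wald interval, the 80% half-width is 1.2816 × √(0.5/35) = 0.153.

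**The case against.** The best defence is that the sentence speaks of interval width. Read as a statement of size only, a full width of at most 2 × 0.157 = 0.314 holds for every count to rounding. On that reading the number is right and the fault is one of notation. This stands as far as it goes: 0.157 is not a calculation error, and anyone who infers one from the mismatch would be wrong. It does not rescue the sentence, which attaches the figure to the observed proportion. Nor does it help for ORR and CBR, where the exact interval is wider even comparing half-width with half-width.

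The defence is also right that the excess is small. A tally of 22 of 36 counts makes a difference of at most 0.009 look larger than it is. For counts of 0 to 6 and 29 to 35 the Wilson statement holds even literally.

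Three stronger readings are tempting, and the documents do not support them.

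- *That the sample size depends on this figure.* Protocol 13.1 says the size was set on clinical grounds. The precision statement only describes the result.
- *That the between-arm intervals breach the stated precision.* The statement is limited to estimates within each arm, and a difference is another quantity. The Protocol's default is "All CIs will be 95%, unless stated otherwise", and a 95% difference interval would be about ± 0.234 (1.960 × √(0.5/35)). The SAP, however, reports differences in proportions at 80%, where the approximate worst case is 0.153.
- *That the SAP uses no Wilson method anywhere.* It names none. But the interval for the adjusted difference is defined only through a cited paper that is not among the documents, so the stronger statement cannot be made.

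**Conclusion.** The binary precision statement is wrong as written in both documents, by a small amount. As a bound around the observed proportion, the Wilson figure should be 0.166. For the per-arm intervals the SAP names, the half-width is up to 0.173 and the limits lie up to 0.179 away. The correct label for 0.157 is the maximum Wilson half-width.

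The result assumes exactly 35 evaluable patients in an arm. SAP 6.2.8.7 also analyses a response-evaluable set, which may be smaller. With 32 patients the largest Clopper-Pearson half-width would be 0.181.

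The 0.153 for a difference is an approximation: both rates are assumed to be 0.5, and the ECOG stratification is ignored. No endpoint, analysis or sample size is affected.

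**What to change.** In Protocol 13.1 and SAP 2.3, replace the binary sentence with wording such as:

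> With 35 patients per arm, the exact (Clopper-Pearson) 95% confidence limits lie at most 0.18 from the observed proportion (half-width at most 0.173).

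Keep ± 0.344 SD for means.

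Optionally, add to the SAP that the 80% interval for the between-arm difference in proportions has a half-width of at most about 0.153, and state the approximation (unstratified Wald, both rates 0.5). Do not add to the SAP a 95% precision for that difference or a precision for a between-arm difference in means. The SAP plans neither interval: differences in proportions are reported at 80%, the blood-count endpoints get descriptive statistics and graphs (SAP 6.2.7.1), and SAP section 7 removes the covariance models.

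The cost is one sentence in each document, with slightly less favourable figures. Design, data collection and analysis do not change.

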### **13.2. General Considerations**

#### **13.2.1. Analysis Populations/Sets**

The full analysis set (FAS) includes all patients who received at least 1 dose of study drug. Analyses using the FAS will be conducted on the basis of the assigned treatment. All efficacy analyses will be assessed using the FAS and the FAS is the primary population for analysis.

The safety population includes all enrolled patients who received at least 1 dose of study drug. The safety population will be conducted on the basis of the actual treatment received. All safety analyses will be assessed using the safety population.

A per-protocol (PP) subset may also be used to analyze select endpoints and will be based on study drug exposure (compliance and/or time on study drug) and major protocol deviations. The criteria for inclusion in the PP subset will be finalized and documented prior to unblinding patients in Part 2 of the study.

The PK set will include all dosed patients in Part 1 with evaluable PK data.

#### **13.2.2. Timing of Analyses**

##### **13.2.2.1. Interim Safety Reviews**

A DMC will monitor accumulating safety data according to a charter that defines its roles and responsibilities. The DMC will perform reviews approximately every 4 months during the Treatment Phase of Part 2, depending upon the enrollment rate. Additional reviews may occur based on DMC requests. The committee will consist of individuals with extensive multicenter clinical study experience drawn from the fields of clinical oncology (specifically, SCLC) and biostatistics. These individuals will be entirely independent of the conduct of the study.

Additional details regarding the committee procedures and policies, including table displays and strategy for maintaining study blind, are described in the DMC charter.

No interim analyses of efficacy are planned.

#### 13.2.2.2. Final Analysis

The final analysis will occur when the last patient completes the Post-Treatment Visit. All study data collected up through the time of the final analysis data cut, including Follow-Up Survival Phase results, will be included in the final analysis. Unblinding will occur at the time of the final analysis.

#### 13.2.2.3. End of Study Analysis

If the Follow-up Survival Phase of the study continues after the final analysis, a supplementary analysis will be done at the time of study completion. Reported results will be cumulative in nature, including all data collected during the entire study.

### 13.2.3. General Considerations for Data Analysis

All statistical analyses will be performed using SAS® version 9 or higher.

Data will be summarized separately by study part (Part 1 and Part 2). Data from Part 1 will be summarized descriptively by dose level if applicable and overall. Data from Part 2 will be summarized descriptively by treatment group and overall. Treatment differences between treatment groups for Part 2 will be calculated as G1T28 + E/P therapy minus placebo + E/P therapy. Select safety summaries will include combined data from both Part 1 and Part 2 of the study. The descriptive summary for the categorical variables will include counts and percentages. The descriptive summary for the continuous variables will include means, medians, standard deviations, and minimum and maximum values. The descriptive summaries of time to event data will include median, twenty-fifth and seventy-fifth percentiles and standard error. All data will be listed for all patients. Unless specified otherwise, safety summaries will include all collected data, and summaries of efficacy will include data collected through the Treatment Phase.

This study is descriptive in nature, and no formal hypothesis testing will be performed across treatment groups. All CIs will be 95%, unless stated otherwise.

The effects of covariates and withdrawal from study treatment due to reasons other than death, disease progression, and toxicity will be assessed to determine the impact on the general applicability of results from this study. Further details of the analysis, including the handling of missing data, impact of variable chemotherapy dose exposure including dose reductions, transformations and other data handling procedures will be provided in a separate SAP. Exploratory analyses of the data will be conducted as deemed appropriate.

Summaries that are based on within-cycle, including changes, events, or findings, will require a clear definition of “end of cycle” that accounts for variable durations in the cycle due to within-cycle dosing delays, delays in subsequent cycle initiation, and incomplete cycles. This will be discussed in the SAP for each applicable endpoint.

Protocol violations will be fully defined and documented before unblinding.

### **13.3. Baseline and Demographic Characteristics**

Demographics and baseline characteristics will be summarized descriptively.

### **13.4. Efficacy Analysis**

#### **13.4.1. Efficacy Endpoints**

Unless otherwise stated, the terminology ‘hematologic parameters’ refers to ANC, lymphocyte, hemoglobin, and platelet counts; the terminology ‘hematologic toxicities’ refers to neutropenia, lymphopenia, anemia, and thrombocytopenia. Each parameter and toxicity will be evaluated individually, but are described as such to avoid repetition. Hematologic toxicities are assigned based on CTCAE, Version 4.03.

- Hematologic kinetic endpoints:
  - Change and percent change in hematologic parameter values from baseline to the Post-Treatment Visit
  - Change and percent change in hematologic parameter values from predose for a particular cycle to the end of that cycle
  - Change and percent change in hematologic parameter values from predose for a particular cycle to nadir for that cycle
  - Rate of change in hematologic parameter values from predose for a particular cycle to nadir for that cycle
  - Change and percent change in hematologic parameter values from nadir for a particular cycle to the end of that cycle
  - Rate of change in hematologic parameter values from nadir for a particular cycle to the end of that cycle
  - Area under the curve in hematologic parameter values from predose for a particular cycle to the end of that cycle
  - Area under the curve in hematologic parameters from predose for a particular cycle to nadir for that cycle
  - Area under the curve in hematologic parameter values from nadir for a particular cycle to the end of that cycle
  - By cycle and overall study hematologic parameter nadir values
  - Time to hematologic parameter value nadir by cycle
  - Time to return to predose hematologic parameter values by cycle
  - Proportion of patients with a return to predose hematologic parameter values by cycle
- Hematologic toxicity endpoints:
  - Incidence of Grade 3 and 4 hematologic toxicities
  - Total number of Grade 3 and 4 hematologic toxicities
  - Proportion of patients with a hematologic toxicity recovery by cycle
  - Time to hematologic toxicity recovery by cycle

- Chemotherapy exposure and compliance endpoints:
  - Duration on treatment
  - Number of cycles received
  - Dose intensity and cumulative dose
  - Incidence of dose interruptions, delays, and reductions
  - Incidence of dose delays due to hematologic toxicity
  - Incidence of study treatment termination due to hematologic toxicity
  
- Other efficacy endpoints:
  - Incidence of infections overall and by severity
  - Incidence of RBC and platelet transfusions
  - Incidence of hematopoietic growth factors use
  - Incidence and duration of systemic antibiotic use
  
- Exploratory efficacy endpoints:
  - Incidence of Grade 2 or greater nephrotoxicity
  - Incidence of alopecia and mucositis
  - Functional Assessment of Cancer Therapy QOL instrument (FACT) total scale score (general)
  - FACT domain scores (physical, social/family, emotional, and functional well-being)
  - FACT-L total scale score
  - FACT-L lung cancer subscale score
  - FACT-L trial outcome index score
  - FACT-An total scale score
  - FACT-An anemia subscale score
  - FACT-An trial outcome index score
  - Composite hematologic score (this will be specified *a priori* in a SAP)
  - Composite efficacy score (this will be specified *a priori* in a SAP)

